This is a prospective study with a Screening Period of 3 to 21 days, an 8-week Double-blind Acute Phase, and a 26-week Double-blind Maintenance Phase. Each phase includes 2 arms, and subjects will be randomized to 1 of 2 doses (low or high) of MMX mesalamine/mesalazine (900-4800mg/day, given once daily) at the beginning of each phase. Randomization will be in a 1:1 ratio stratified by body weight group. There is an additional 8-week, Open-label Acute Phase for subjects who do not achieve a clinical response or who have withdrawn from the Double-blind Acute Phase after a minimum of 2 weeks and, in the investigator's opinion, have not benefited from treatment in the Double-blind Acute Phase. Clinical response is defined as partial Ulcerative Colitis Disease Activity Index (UC-DAI) \leq 1 (with rectal bleeding=0 **and** stool frequency \leq 1 **and** Physician's Global Assessment [PGA]=0) at the end of the Double-blind Acute Phase. In this Open-label Acute Phase, subjects are treated with the high dose of MMX mesalamine/mesalazine for their weight group.

At the Baseline Visit (Visit 2):

- Subjects with partial UC-DAI \geq 2 (with a combined rectal bleeding **and** stool frequency score \geq 1 **and** PGA=1 or 2) **and** with mucosal appearance (endoscopy score)=2 or 3 will be eligible to enter the Double-blind Acute Phase.
- Subjects with partial UC-DAI \leq 1 (with rectal bleeding=0 **and** stool frequency \leq 1 and PGA=0) **and** with mucosal appearance (endoscopy score)=0 or 1 will be eligible to enter the Double-blind Maintenance Phase.

Subjects with partial UC-DAI score between 1 and 2 will not be eligible to enter the Double-blind Acute Phase or the Double-blind Maintenance Phase.

A minimum of 1 score each for stool frequency and rectal bleeding must be available in order to randomize subjects into either the Double-blind Acute Phase or the Double-blind Maintenance Phase. Subjects with no symptom score data available will be considered screen failures as these symptom score data are used to calculate the partial UC-DAI score needed for enrollment.

Subjects who do not meet all the eligibility criteria for either the Double-blind Acute Phase or the Double-blind Maintenance Phase will be considered screen failures. Subjects may be rescreened after consultation with the medical monitor.

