Double-blind Maintenance Phase:

30. Mucosal appearance (endoscopic score)=2 or 3 based on central reading or local reading (if central reading is not available) at the Screening Visit (Visit 1) or Baseline Visit (Visit 2).

Re-randomization: Subjects with a clinical response, ie, partial UC-DAI \leq 1 (defined as rectal bleeding=0 **and** stool frequency \leq 1 **and** PGA=0) after completion of treatment in either the Double-blind or the Open-label Acute Phases will be eligible for re-randomization into the Double-blind Maintenance Phase provided they still meet all Baseline (Visit 2) inclusion and exclusion criteria (where re-assessed).

Note that an additional eligibility endoscopy is not required for entry into the Double-blind Maintenance Phase for subjects who achieve a clinical response after completion of treatment in either the Double-blind Acute Phase or the Open-label Acute Phase.

Subjects eligible for either the Double-blind Acute or the Double-blind Maintenance Phase can be re-randomized if they initially failed randomization for the following reasons: incorrect use of IVRS, late or missing central laboratory or endoscopy results, or other reasons of this type as long as they meet inclusion and exclusion criteria. Re-randomization can only take place after consultation with the medical monitor.

Subjects may be re-randomized into the Double-blind Maintenance Phase if they turned 18 during participation in either Acute Phase of the study.

Maximum duration of subject involvement in the study:

- Planned duration of screening period: 3 to 21 days
- Planned duration of treatment period: up to 42 weeks
- Planned duration of follow-up: 7 days

Endpoints and statistical analysis:

Primary Efficacy Endpoints

Double-blind Acute Phase:

The primary efficacy endpoint for the Double-blind Acute Phase is defined as the proportion of subjects with a clinical response (defined as partial UC-DAI ≤ 1 with rectal bleeding=0 **and** stool frequency ≤ 1 **and** PGA=0) at Week 8. This endpoint will be compared between treatment arms using a continuity-corrected chi-squared test.

Double-blind Maintenance Phase:

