6.2.3 Dosing

Subjects entering the Double-blind Acute Phase or entering the Double-blind Maintenance Phase directly will be randomized to low- or high-dose MMX mesalamine/mesalazine stratified by their weight group at the Baseline Visit (Visit 2).

Subjects entering the Double-blind Maintenance Phase after completing 1 or both of the Acute Phases will be re-randomized to low- or high-dose MMX mesalamine/mesalazine at the start of the Double-blind Maintenance Phase at Visit 3.2 (Week 8 of the Double-blind Acute Phase) or 4.2 (Week 8 of the Open-label Acute Phase), as applicable, based on their weight at the time of re-randomization.

Doses will be as follows:

- 900 or 1800mg/day for subjects weighing 18 to \leq 23kg
- 1200 or 2400mg/day for subjects weighing >23 to \leq 35kg
- 1800 or 3600mg/day for subjects weighing >35 to \leq 50kg
- 2400 or 4800mg/day for subjects weighing >50 to \leq 90kg.

Subjects participating in the Open-label Acute Phase will receive the high dose for their weight group. The subject's weight at Visit 3.2 (Week 8/Withdrawal of the Double-blind Acute Phase) will be used to determine the high dose assigned to the subject.

Investigational product will be administered orally, once daily, in accordance with the MMX Mesalazine (Mesalamine) Investigator's Brochure. No titration or dose adjustment is allowed.

Dosing with investigational product will begin the day of the Baseline Visit (Visit 2) if the subject's currently prescribed 5-ASA treatment (if applicable) has not yet been taken that day. If the subject's currently prescribed 5-ASA treatment (if applicable) has been taken the day of the Baseline Visit (Visit 2), dosing with investigational product will begin the day after the Baseline Visit (Visit 2).

When proceeding through study phases, dosing with newly prescribed investigational product will begin the day of the study visit if the subject's currently prescribed investigational product from the current phase has not yet been taken that day. If the subject's currently prescribed investigational treatment has been taken the day of the study visit, dosing with newly prescribed investigational product will begin the day after the first study visit of the new phase.

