5.9 Analysis of Safety

All summaries of safety data will be produced separately for each phase of the study, for the Double-blind Acute Safety Analysis Set (overall and by treatment arm), Open-label Acute Safety Analysis Set (by treatment arm only), and Double-blind Maintenance Phase Safety Analysis Set (overall and by treatment arm).

Baseline is defined as the last observation prior to first dose of investigational product in the study. If an assessment occurs on same day as the first dose of investigational product, the assessment will be considered the Baseline assessment. The Double-blind Acute Phase Week 8/Withdrawal visit (Visit 3.2) is treated as the Open-label Acute Phase Week 0 for subjects continuing into the Open-label Acute Phase from this visit. The Double-blind Acute Phase Week 8/Withdrawal visit (Visit 3.2) is treated as the Double-blind Maintenance Phase Week 0 for subjects continuing into the Double-blind Maintenance Phase from this visit. The Open-label Acute Phase Week 8/Withdrawal visit (Visit 4.2) is treated as the Double-blind Maintenance Phase Week 0 for subjects continuing into the Double-blind Maintenance Phase from this visit. For subjects who enter the Double-blind Maintenance Phase directly, the Baseline Visit (Visit 2) is treated as the Double-blind Maintenance Phase Week 0.

Safety variables include AEs, clinical laboratory variables and vital signs variables. For each safety variable, the last value collected prior to the first dose of investigational product (during phase of interest) will be used as baseline/Week 0 for the analyses of that safety variable. A Final on-Treatment Assessment (FoTA) will be defined as the last valid assessment obtained after baseline/Week 0 and whilst on investigational product.

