5.9.1 Adverse Events

Adverse events will be coded using Version 16.1 (or newer) of Medical Dictionary for Regulatory Activities (MedDRA). The number and percentage of subjects with an event, as well as the number of events will be reported for each summary.

An AE (classified by preferred term) that occurs during the study will be considered a treatment-emergent AE (TEAE) if it has a start date on or after the first dose of investigational product or if it has a start date before the date of the first dose of investigational product, but increases in severity on or after the date of the first dose of investigational product. If more than 1 AE with the same preferred term is reported before the date of the first dose of investigational product, then the AE with the greatest severity will be used as the benchmark for comparison to the AEs occurring during the study under the preferred term. An AE that occurs more than 7 days after the date of the last dose of investigational product of that phase will not be counted as a TEAE.

An overall summary of the number of subjects with TEAEs and number of TEAEs will be presented overall for the Overall Safety Analysis Set, an overall summary of the number of subjects with TEAEs and number of TEAEs will be presented for High-dose MMX only for Open Label Acute Phase Safety Analysis Set, and by treatment group and overall for the Double-blind Acute and Double-blind Maintenance Phase Safety Analysis Sets. The summary will include the number and percentage of subjects with any TEAEs, serious TEAEs, TEAEs related to investigational product, TEAEs leading to discontinuation of investigational product and TEAEs leading to death.

The number and percentage of subjects reporting TEAEs, as well as the number of events, will be tabulated by system organ class (SOC) and preferred term for Overall Safety Analysis set, the Double-blind Acute and Double-blind Maintenance Phase Safety Analysis Sets, and also for Open-label Acute Phase Safety Analysis Set.

The number and percentage of subjects reporting TEAEs will also be tabulated by SOC, preferred term, and maximum severity for Overall Safety Analysis set, Double-blind Acute and Double-blind Maintenance Phase Safety Analysis Sets, and also for Open-label Acute Phase Safety Analysis Set.

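### The 7-day TEAE tail of one phase runs into the first week of the next, so an AE can be counted in two phase tables and charged to a dose already left; the effect on the dose contrast is modest

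*SAP*

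**What the plan says.** SAP 5.9.1 counts an AE as treatment-emergent "if it has a start date on or after the first dose of investigational product", or if it began earlier and became more severe on or after that dose. The only upper limit is that an AE occurring "more than 7 days after the date of the last dose of investigational product of that phase will not be counted as a TEAE". SAP 5.9 adds: "All summaries of safety data will be produced separately for each phase of the study", with results by arm in the two double-blind phases.

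Protocol 6.2.3 leaves no gap between phases. "When proceeding through study phases, dosing with newly prescribed investigational product will begin the day of the study visit" if the current product has not yet been taken that day. Otherwise, "dosing with newly prescribed investigational product will begin the day after the first study visit of the new phase".

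Protocol 9.9 leaves the TEAE definition to the SAP. Neither document ends the tail at the next phase's first dose, or says which phase owns an AE that starts in the overlap. The table titles in SAP section 10 place TEAEs *during* a phase without defining the word. After an acute phase, the follow-up contact within 7 days of last dose applies only to children leaving the study (footnotes to Protocol Tables 1 and 2). The SAP tail has no such limit.

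**The concern.** A tail after last dose is meant to catch events that appear once drug has stopped. Here, a child who continues has not stopped drug and may have moved to another dose. All open-label treatment is at the high dose (Protocol 6.2.3), so an AE in a low-arm child's first open-label week starts on the high dose yet meets the low-arm Double-blind Acute definition. The same can happen at entry to maintenance, where the dose is randomised afresh.

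Evaluating the safety and tolerability of the low and high doses in each phase is a stated objective (Protocol 2.2.2, SAP 2.2.3), and the phase-by-arm TEAE tables are how it is reported. With small arms, one misplaced child can matter in a single row. At about 26 or 27 per arm, a preferred term going from one child to two moves from 3.8% to 7.5%, across the 5% threshold for the table of frequent events in SAP 5.9.1.

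**Working it through.** **1. Is there a gap between phases?** The protocol synopsis gives "an 8-week Double-blind Acute Phase, and a 26-week Double-blind Maintenance Phase" and states: "There is an additional 8-week, Open-label Acute Phase". The sum is 8 + 8 + 26 = 42 weeks. This reproduces the synopsis figure exactly ("Planned duration of treatment period: up to 42 weeks"), so there is no washout.

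**2. Day count.** Put the transition visit on day 56 and apply both dosing-start rules of Protocol 6.2.3.

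| Old product on visit day | Last old dose | First new dose | Old window ends (last dose + 7) | Overlap |
|---|---|---|---|---|
| Not taken | day 55 | day 56 | day 62 | days 56–62 = 7 days |
| Taken | day 56 | day 57 | day 63 | days 57–63 = 7 days |

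Either way, the overlap is days 1–7 of the new phase. If the old window ends on the day before the first new dose, the overlap is 0 days.

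**3. Share of the windows.**
- Of the Double-blind Acute window after a full 8 weeks: 7/63 = 11.1%. For a move to open label at Week 4: 7/35 = 20%. At the Week 2 minimum: 7/21 = 33%.
- Of the phase being entered: 7/56 = 12.5% of a full Open-label Acute Phase and 7/182 = 3.8% of maintenance.

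**4. Who changes dose?** Every low-arm child entering open label does. Of the 28 rollovers expected into maintenance (Protocol 9.6), 1:1 re-randomisation puts about 28 × 0.5 = 14 on a different dose level from the phase just left. The documents give no AE rates. At an assumed 0.05 to 0.20 AEs per child-week, the one-week overlap at maintenance entry gives 28 × 0.05 = 1.4 to 28 × 0.20 = 5.6 AEs in two phase tables. Of these, 14 × 0.05 = 0.7 to 14 × 0.20 = 2.8 are also charged to a dose level already left.

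**5. Effect on the low-versus-high contrast in the acute phase.** Assumptions, none from the documents: constant hazards; low-arm 8-week incidence 20%; high-dose hazard twice the low-dose hazard; switching at Week 8 by the same fraction *f* of each arm, with *f* = 0.6 or 1.

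λ = −ln(0.8)/56 per day on the low dose and 2λ on the high dose.

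- No tail: low 20.0%; high 1 − exp(−112λ) = 36.0%.
- Low-arm switcher, 56 low-dose days plus 7 high-dose days: 1 − exp(−(56 + 14)λ) = 24.3%.
- High-arm switcher, 63 high-dose days: 1 − exp(−126λ) = 39.5%.
- At *f* = 0.6: low 0.4 × 20.0 + 0.6 × 24.3 = 22.6%; high 0.4 × 36.0 + 0.6 × 39.5 = 38.1%.

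| Switching in each arm | Low | High | Difference | Ratio |
|---|---|---|---|---|
| No tail | 20.0% | 36.0% | 16.0 points | 1.80 |
| 60% | 22.6% | 38.1% | 15.5 points | 1.68 |
| 100% | 24.3% | 39.5% | 15.1 points | 1.62 |

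**6. How much of the low-arm rise comes from the dose change?** A 7-day tail at an unchanged low-dose hazard gives 1 − exp(−63λ) = 22.2%. In the 100% case, about 2.2 of the 4.3 points are therefore extra counted time and about 2.1 come from the dose change.

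**7. In children.** SAP 3.5 reduces the acute phase to 53 subjects, or 53/2 = 26.5 per arm. The low-arm rise of 2.6 to 4.3 points is 26.5 × 0.026 = 0.7 to 26.5 × 0.0434 = 1.2 children.

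**The case against.** The best defence is that phase assignment by onset is plainly intended. The table titles say *during* a phase, and SAP 5.9.1 ties its exclusion to a particular phase. That reading is plausible, but the SAP does not state it. If *during* ended at the last dose, the 7-day tail would add nothing to any phase table, so the word cannot settle the matter.

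A reader might infer that the lower limit is the first dose of the whole study, so that all earlier AEs flow into every later phase table. The documents do not support so flat a statement. SAP 5.9.1 does not say which first dose it means, and SAP 5.9, which lists AEs among the safety variables, sets their baseline by the first dose in the phase of interest. Nor does the overlap depend on this: a phase-specific start would place the event in the new phase without removing it from the old one.

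A reader might also infer from the low arm alone (20% reading 22.6% or 24.3%) that the dose contrast is badly diluted. That overstates it. High-arm children who continue gain the same tail, and about half of the low-arm rise is only longer counting. The 100% case also requires that no low-dose child responds or leaves the study.

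It is fair, too, that the TEAE tables are descriptive in an unpowered estimation study, and that all AEs are listed, as is exposure by subject and phase, so an affected event can be traced. And the dose at onset is itself a convention: an event on day 1 or 2 of a new phase may reflect the previous dose. These points limit the weight of the problem. None of them supplies the missing cut-off.

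**Conclusion.** The point stands as a defect in a stated rule. As written, an AE with onset in days 1 to 7 of a new phase meets the TEAE definition of the phase just left as well as that of the new one. The wrong dose is charged only where the dose level changed; otherwise the event sits in two phase tables at the same dose level. The Overall Safety Analysis Set summaries are not split by phase, so the overlap causes no double count there. Direct maintenance entrants and children leaving after one phase are not touched.

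The effect on the low-versus-high contrast is modest: about 0.5 to 0.9 points off a 16-point difference, a ratio of 1.68 to 1.62 instead of 1.80, and a low-arm shift of about one child. These figures rest on the assumed doubled hazard, 20% incidence, switching at Week 8 and equal switching in both arms. If fewer high-arm than low-arm children move to open label, the difference narrows more; the documents give no switching rates. The overlap of 7 days rests on no assumption beyond the two dosing-start rules. The correction should be made because it is cheap and removes an avoidable misattribution, not because the safety conclusions are shown to be unsound.

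**What to change.** Amend SAP 5.9.1 as follows:

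- Define a TEAE of a phase as an AE with onset or worsening on or after the first dose in that phase and before the first dose of the next phase.
- Apply the 7-day tail only to subjects who take no further investigational product.
- Assign an AE that starts in one phase and worsens after the next phase's first dose to the later phase, as a worsening event. This fits Protocol 8.1.1, which already records a change in severity as a new event.

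State also that the table titles' *during* refers to this definition. The overlap then falls from 7 days to 0, and children who leave the study keep their full 7-day window.

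The cost is a few sentences and a short programming change, with no new data. The downside is that events in the first days of a new phase that reflect the previous dose will be attributed to the new one; the SAP should say so.

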5.9.2 Clinical Laboratory Variables

Descriptive statistics for clinical laboratory values (in SI units) and changes from baseline at each assessment time point as well as shift tables from baseline/week 0 to each visit for quantitative variables will be presented for the following clinical Hematology and Biochemistry laboratory variables (Note: Urinalysis is only collected at screening and will be listed but not summarized) for Double-blind Acute and Double-blind Maintenance Phase Safety Analysis Sets, and also for Open-label Acute Phase Safety Analysis Set .

Hematology Complete blood count (RBC [red blood cells], WBC [white blood cells], platelets, HGB [hemoglobin]), HCT (hematocrit), white blood cell differential

Biochemistry ALT, albumin, alkaline phosphatase, AST, bilirubin (total), bicarbonate, calcium, chloride, cholesterol (total), creatinine (enzymatic), CK (creatinine kinase), CRP standard (C-reactive protein), direct bilirubin, gamma glutamyl transpeptidase (GGT), glucose random (serum), lactate dehydrogenase, magnesium, phosphate, potassium, sodium, total protein, triglycerides, urea (BUN, blood urea nitrogen), uric acid

Urinalysis Bilirubin, blood, glucose, ketones, pH, protein, specific gravity

Clinical laboratory test values are potentially clinically important (PCI) if they meet either the low or high PCI criteria listed in [Table 2](#). The number and percentage of subjects with post-baseline/Week 0 PCI values during phase of interest will be tabulated. The percentages will be calculated relative to the number of subjects with available baseline/Week 0 values and at least 1 post-baseline/Week 0 assessment during phase of interest.

The numerator is the total number of subjects with at least 1 post-baseline/Week 0 PCI value during phase of interest. A supportive listing of subjects with post-baseline PCI values will be provided including the subject number, site, baseline/Week 0, and post-baseline/Week 0 values.

Table 2: Criteria for Potentially Clinically Important Laboratory Tests

Parameter	SI Unit	Lower Limit	Higher Limit
Biochemistry			
Sodium	mmol/L	<130	>150
Potassium	mmol/L	<3.0	>5.5
Glucose	mmol/L	<3.1	>8.6
Blood Urea Nitrogen	mmol/L	-	>1.5 x ULN
Creatinine	µmol/L	-	>1.5 x ULN
Calcium	mmol/L	<2.20 (2-11 yrs) <2.10 (12-17 yrs) <2.00 (>17 yrs)	>2.82 (2-11 yrs) >2.67 (12-17 yrs) >2.87 (>17 yrs)
Total Protein	g/L	<54	>86
Albumin	g/L	<33 (5-14 yrs) <33 (15-17 yrs, F) <30 (15-17 yrs, M) <30 (>17 yrs)	-
Aspartate Transaminase (AST)	U/L	-	>1.5 x ULN
Alanine Transaminase (ALT)	U/L	-	>1.5 x ULN
Gamma Glutamyl Transferase (GGT)	U/L	-	>1.5 x ULN
Alkaline Phosphatase	U/L	-	>1.5 x ULN
Total Bilirubin	µmol/L	-	>1.5 x ULN
Bicarbonate	mmol/L	<16	>30
Chloride	mmol/L	<90	>115
Uric acid	µmol/L	-	>532 (F) >591 (M)
Phosphate	mmol/L	<1.01 (3-9 yrs) <1.04 (10-15 yrs) <0.75 (>15 yrs)	>2.06 (3-9 yrs) >1.93 (10-15 yrs) >1.61 (>15 yrs)
Triglycerides	U/L	-	>2.5 x ULN
Lactate dehydrogenase (LDH)	U/L	-	>2.5 x ULN
Creatine kinase	U/L	-	>1.5 x ULN
Magnesium	mmol/L	<0.74	-

Table 2: Criteria for Potentially Clinically Important Laboratory Tests

Parameter	SI Unit	Lower Limit	Higher Limit
Cholesterol	mmol/L	-	>7.77
Hematology			
White Blood Cell Count – Total (WBC)	$10^9/L$	<4.10 (3-4 yrs) <3.60 (5-6 yrs) <3.10 (7-8 yrs) <3.00 (>8 yrs)	>19.20 (3-4 yrs) >18.00 (5-6 yrs) >17.00 (7-8 yrs) >16.50 (9-10 yrs) >16.20 (11-15 yrs) >16.00 (>15 yrs)
Red Blood Cells (RBC)	$10^{12}/L$	<3.0	-
Hemoglobin	g/L	<100	-
Hematocrit	L/L	<0.32	>0.50
Platelet Count	$10^9/L$	<75	>500
Neutrophils/Leukocytes	%	<20 (2-5 yrs) <25 (6-11 yrs) <30 (12-17 yrs) <40 (>17 yrs)	>65 (2-11 yrs) >70 (12-17 yrs) >75 (>17 yrs)
Lymphocytes/ Leukocytes	%	<12 (2-17 yrs) <15 (>17 yrs)	>63 (2-5 yrs) >57 (6-11 yrs) >52 (12-17 yrs) >47 (>17 yrs)
Monocytes/Leukocytes	%	-	> 15
Eosinophils/Leukocytes	%	-	> 10
Basophils/Leukocytes	%	-	> 10

LLN: Lower limit of normal value provided by the laboratory

ULN: Upper limit of normal value provided by the laboratory

